1.1.1 Definity Clinical Safety

Definity is well tolerated and has been used extensively in echocardiography applications [Goldberg et al 2001]. In pre-market clinical trials, Definity was administered to 1716 patients. In these patients 269 (8.4%) reported at least one adverse event (AE). Of these events, 26 were classified as serious including 19 (1.1%) patients experiencing serious cardiopulmonary symptoms including eight deaths. The deaths occurred several days after activated Definity administration and appear to be related to the course of underlying disease. Of the 11 other serious AEs, which appeared within days of the drug administration (2-15 days), all appeared to be a progression of underlying cardiac and non-cardiac disease. However, a role for Definity in the initiation or course of these AEs cannot be ruled out. Of the reported adverse reactions following the use of Definity the most frequently reported were headache (2.3%), back and renal pain (2.1%), flushing (1.1%), and nausea (1.0%). Additional risks associated with the contrast material are described in the attached Definity Product insert (Appendix B). All of the non-serious reported side-effects have been transient, usually lasting only a few minutes.

Table 1.

Selected Adverse Events Reported in $\geq 0.5\%$ of the Subjects who Received Definity in Controlled Clinical Studies

No. of Patients Exposed to Definity	1716	
No. of Patients Reporting an Adverse Event	269 (8.8%)	
Central and peripheral nervous system	54	(3.2%)
Headache	40	(2.3%)
Dizziness	11	(0.6%)
Body as a Whole	41	(2.4%)
Back/Renal Pain	20	(1.2%)
Chest Pain	13	(0.8%)
Digestive System	31	(1.8%)
Nausea	17	(1.0%)
Vascular (extracardiac) disorders	19	(1.1%)
Flushing	19	(1.1%)
Application Site Disorders	11	(0.6%)
Injection Site Reactions	11	(0.6%)

Additional information concerning pre-clinical and clinical experience with Definity, including the dosing levels and reported subject complaints, can be found in section 6.5 and the Definity Package Insert that is included as Appendix B.

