6.6.2 Adverse Events

An AE includes any condition that was not present prior to trial treatment, but appeared following initiation of trial medication; any condition that was present prior to trial treatment, but worsened during trial medication; or any condition, of which the subject has a history, that was not present prior to trial medication initiation but reappeared following administration of Definity. This would include conditions that are likely to be associated with an underlying or intermittent disease (e.g., angina, flu, etc.).

The subjects will be monitored for AEs during the entire procedure. All AEs, including observed or volunteered problems, complaints, signs or symptoms, and diagnoses, occurring from the initiation of

Definity dosing until the completion of the Definity administration will be recorded on a serious or non-serious AE data form, whether or not associated with the use of the trial medication. GE Healthcare will be informed of all AEs. In addition all unexpected and serious AEs are reported to the TJU IRB and to the FDA. The investigator is required to submit all unexpected and serious AEs to the TJU IRB within 48 hours, and to GE Healthcare. Fatal AEs related to treatment which are unexpected must be reported within 24 hours to the TJU IRB and to GE Healthcare. Fatalities not related to the study drug/device must be reported within 5 days. The PI of the study has previous experience running ultrasound clinical trials and will serve as the study sponsor. He will be responsible for ensuring all FDA requirements are met and all AE are properly reported.

The AE forms will include: subject identification number and initials; subject's date of birth, gender, and ethnicity; name of the institution, date of Definity administration; signs/symptoms and severity; date of onset; date of resolution or death; relationship to the study drug; action taken; concomitant medication(s) including dose, and route and duration of treatment.

Whenever possible, the AE will be evaluated and reported as a diagnosis rather than individual signs and symptoms. If a definitive diagnosis is not possible, the individual signs and symptoms will be recorded. The investigator(s) will evaluate and note the duration, intensity, and relationship to (association with) the Definity administration, the action taken, and the determination of seriousness for each AE.

INTENSITY OF AEs

The intensity of the AE will be characterized as mild, moderate, or severe.

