Mild AEs are usually transient, require no special treatment, and do not interfere with the subject's daily activities.

Moderate AEs traditionally introduce a low level of inconvenience or concern to the subject and may interfere with daily activities but are usually ameliorated by simple therapeutic measures.

Severe AEs interrupt a subject's usual daily activity and typically require systemic drug therapy or other

treatment.

When the intensity of the AE changes over time, the maximum intensity will be recorded.

RELATIONSHIP TO DEFINITY ADMINISTRATION

The relationship or association of the AE to the Definity administration will be characterized as "unlikely," "possible," or "probable." A relationship assessment will be performed by the investigator to determine if an AE is attributable to Definity and will be recorded on a data form. The investigator will refer to the Definity investigator brochure for assistance in determining AE relationship.

An "unlikely" relationship indicates that there is little or no chance that Definity caused the reported AE; other conditions, including concurrent illnesses, progression or expression of the disease state, or a reaction to a concurrent medication, appear to explain the reported AE.

A "possible" relationship indicates that the association of the AE with Definity is unknown. However, the AE is not reasonably attributed to any other condition.

A "probable" relationship indicates that a reasonable temporal association exists between the AE and Definity administration and, based upon the investigator's clinical experience, the association of the event with the trial medication seems likely.

SERIOUS ADVERSE EVENTS

A serious AE is defined as a significant clinical hazard, contraindication, or precaution that:

- Results in death
- Is life-threatening (In the opinion of the investigator, there is an immediate risk of death from the AE as it occurred. This does not include an AE that had it occurred in a more serious form may have caused death.)
- Results in a persistent or significant temporary disability/incapacity defined as a substantial disruption of a person's ability to conduct normal life functions
- Results in or prolongs an existing in-patient hospitalization (an overnight stay in the hospital, regardless of length) [Note: A hospitalization for an elective procedure or treatment which is

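### The definition of a possible relationship leaves no category for an adverse event with a plausible Definity role and a reasonable competing cause

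*Combined protocol and SAP*

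**What the plan says.** Section 6.6.2 gives causality to the investigator: "A relationship assessment will be performed by the investigator to determine if an AE is attributable to Definity". Three grades are offered and no others.

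- *Unlikely*: such a "relationship indicates that there is little or no chance that Definity caused the reported AE". The definition goes on to list concurrent illness, the disease itself and other medication as things that "appear to explain the reported AE".
- *Possible*: such a "relationship indicates that the association of the AE with Definity is unknown". The next sentence adds a restriction: "However, the AE is not reasonably attributed to any other condition".
- *Probable*: the timing is reasonable and, in the investigator's clinical experience, the link seems likely. Other causes need not be excluded.

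The same section sets three reporting times. On deaths: "Fatal AEs related to treatment which are unexpected must be reported within 24 hours" and "Fatalities not related to the study drug/device must be reported within 5 days". Separately, all unexpected and serious adverse events go to the IRB within 48 hours, whatever their cause.

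**The concern.** A causality scale should give every event exactly one place. The restriction on *possible* removes the usual place for an event with two credible explanations, where the drug is a genuine candidate but not the favoured one. The protocol expects competing causes: its definition of an adverse event in Section 6.6.2 expressly takes in conditions linked to an underlying or intermittent disease.

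The adverse event form still asks for a relationship. An investigator facing such an event must stretch one of the definitions, and two investigators could stretch different ones. *Unlikely* is the only definition that accommodates a competing condition, so the likeliest error is towards under-attributing events to Definity. This is an off-label use of the agent, for which the study's safety record is part of what a later, larger study would draw on.

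The reporting rules add a second problem. They turn on whether a death is related or not related, and those words are never tied to the three grades.

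**Working it through.** The protocol gives no figure to reproduce here, so the check is one of logic followed by one of timing.

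**Do the three definitions cover every event?** Two judgements define a case: how strong the Definity link is, and whether another condition is a reasonable explanation. Section 6.6.2 is applied to each combination.

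| Definity link | Another reasonable cause | Grade under Section 6.6.2 |
|---|---|---|
| Little or none | Yes | Unlikely |
| Little or none | No | Unlikely by its first clause; its second clause is not met |
| Plausible or unknown, not likely | No | Possible |
| Plausible or unknown, not likely | Yes | None |
| Likely, timing reasonable | Yes or no | Probable |

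The fourth row fails each definition in turn. It is not *possible*, because another attribution is reasonable. It is not *unlikely*, because the chance of a Definity role is more than little. It is not *probable*, because the link is not judged likely.

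**What time limit would apply to an unexpected death in the fourth row?** The three limits come from Section 6.6.2, with 5 days = 5 × 24 = 120 hours.

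- Treated as related: 24 hours.
- Treated as not related, with the 5-day rule governing: 120 hours, which is 120 − 24 = 96 hours later.
- Treated as not related, with the 48-hour rule governing: 48 hours to the IRB, which is 48 − 24 = 24 hours later.

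The section does not say whether the 48-hour or the 5-day rule prevails for an unexpected death judged unrelated. A related but expected death comes under neither of the two fatality rules.

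**How many events could be involved?** Section 6.5.1 quotes a treatment-related rate of 8.4% from pre-market trials and a drug-related rate of 3.5% from a later registry. If either rate carried over to 45 women, the expected number with a related event would be 45 × 0.084 = 3.8 or 45 × 0.035 = 1.6. These figures only show that the counts are small. The documents do not allow an estimate of how many events would fall in the fourth row.

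**The case against.** The strongest reply is that the gap is narrow and its consequences limited. Several parts of that reply stand.

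- A reader might infer that any event with two plausible causes has no grade. That is too broad. *Probable* stays open when the Definity link seems likely, and *unlikely* properly takes an event with only a small residual chance. Only the middle case is left out.
- A reader might infer that the protocol sends these events to *unlikely*. It does not, and by its own terms *unlikely* does not fit them. Coding there is a plausible default. An investigator might instead read the restriction on *possible* as met when neither cause can be preferred.
- A reader might infer that such a death automatically gets the 5-day limit. The documents never equate *unlikely* with not related, and on its face the 48-hour rule covers an unexpected death regardless of cause.
- No event disappears. All adverse events in the recording period are recorded whether or not they are associated with Definity, and the final report to the IRB under Appendix A lists them all. No hypothesis or analysis in Section 7.2 uses a drug-related event rate.
- Recording stops when Definity administration is complete, within an imaging session of about an hour (Section 3.1). Few deaths would arise in that period, so the practical effect is mainly on the grading of non-fatal events.

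The medical monitor is a partial safeguard. The monitor comments on relationship, but only for serious and unexpected events, within 10 calendar days and therefore possibly after all three limits have passed, and with no different definitions to apply. None of this supplies a grade for the middle case or says what counts as related.

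**Conclusion.** The point holds in a limited form. As written, the scale in Section 6.6.2 is not exhaustive: an event with a plausible but not likely Definity role and a reasonable competing cause has no grade. This follows from the definitions and rests on no numerical assumption. That such events would be coded *unlikely*, and so under-attributed, is a risk that rests on how investigators would resolve the gap. A later death report is likewise a risk. It would be 24 or 96 hours later, depending on which rule governs, and only if *unlikely* is read as not related.

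It is tempting to size the problem from the pre-market experience in Section 1.1.1, where serious events put down to underlying disease carry the remark that "a role for Definity in the initiation or course of these AEs cannot be ruled out". That remark shows the kind of judgement involved, but it does not give a frequency for this study. Those events came days after dosing (2 to 15 days for the 11 that were not deaths), outside this protocol's recording period. Some could fairly be graded *unlikely*, since a role that cannot be excluded may still be a small one. Nor can the 19 and the 26 in that section be made into a proportion, because the first counts patients and the second counts events.

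This does not affect the imaging objectives. It affects the consistency of the safety record and the clarity of a reporting duty, and it is cheap to correct.

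**What to change.** In Section 6.6.2:

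1. Redefine *possible* as a relationship to Definity that cannot be ruled out, even though another condition may also explain the event.
2. Keep *unlikely* for events with little or no chance of a Definity cause. Add that this grade takes precedence where the remaining chance is only slight, so that it does not overlap with the new *possible*. Every event short of *probable* then has one place.
3. State that *possible* and *probable* count as related for reporting.
4. Reconcile the 24-hour, 48-hour and 5-day rules: say which governs when more than one applies to a death, and what applies to a death that is related but expected.

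The cost is a few sentences, matching instructions on the adverse event form, and the amendment approval that Appendix A requires. No study procedure changes. The downside is that somewhat more events will be counted as related to Definity.

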6.7 End-of-Treatment and End-of-Trial Evaluations

6.7.1 Discontinuation of Subjects

Subjects will be free to discontinue trial participation at any time. The investigator will also discontinue any subject from the trial if, in the investigator's opinion, it is not safe for the subject to continue. The date the subject is withdrawn from a treatment and/or from the trial and the reason for discontinuation will be recorded on the CRF.

Trial participation will be considered completed if the subject has met all of the following trial requirements:

- Has received one bolus injection and one infusion of Definity
- Has undergone the complete ultrasound imaging study as described in this protocol

If a subject's participation in the trial is interrupted for any reason (e.g., because of an AE or if the subject is lost to follow-up) and the subject has met the criteria described above for completing the trial, the subject's trial participation will be considered completed. If a subject's trial participation is interrupted for any reason

by the subject's or investigator's choice and the subject has not met all of the criteria listed above, then the subject will be considered a discontinued subject.

7. DATA MANAGEMENT AND STATISTICAL ANALYSES

7.1 Data Management

Data forms will be completed for all subjects enrolled in the trial. The patient study files will be stored in a secure file cabinet and maintained by the research study coordinators at TJU. Patient study files will be kept for 7 years after the completion of the study. The PI of the study has previous experience running ultrasound clinical trials and will serve as the study sponsor. He will be responsible for ensuring all FDA requirements are met and all AE are properly reported.

The final data will be entered into a database. The investigator will be responsible for management of the database. The database will be maintained within an organized and secure directory system.

7.2 Statistical Analyses

7.2.1 Hypotheses

H₁: EV SHI will significantly differentiate malignant from benign adnexal masses using surgical pathology as the reference standard. As an initial end-point we speculate that an area under the ROC curve of 0.75 or better will be achieved by EV SHI.

H₂: EV SHI biomarkers will improve the characterization of benign and malignant adnexal masses compared to standard ultrasound or contrast enhanced MRI or other clinical parameters. As an initial end-point we speculate that an area under the ROC curve of 0.75 or better will be achieved by EV SHI, which will be better than low-end estimates of the accuracy of standard ultrasound, contrast enhanced MRI and other clinical parameters (which is on the order of 0.70 to 0.72).

H₃: A correlation coefficient of 0.70 will be achieved between *in vivo* SHI ovarian neovascularity measurements and iMVD.

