2. TRIAL OBJECTIVES

Trial Objectives: The primary objective of this trial is:

- To develop qualitative subharmonic imaging (SHI) or SHI-derived quantitative biomarkers and **to generate pilot data for a study to evaluate if they improve the characterization of benign and malignant adnexal masses compared to standard ultrasound or contrast enhanced magnetic resonance imaging (MRI) or the risk of malignancy index (RMI).**

and a secondary objective is:

- To compare the SHI depiction of adnexal masses' neovascularity in humans to intra-tumoral microvascular density (iMVD) obtained from CD31 an immunohistochemical marker of angiogenesis.

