6.4 Efficacy Assessments

The pre- and then post-contrast ultrasound imaging will be evaluated for each patient as follows: grayscale, grayscale and PDI (baseline), and grayscale and SHI. While this may introduced some bias from pre- to post-contrast results, we considered this the more realistic approach to how CEUS may be used in clinical practice. Each case will be read independently by the 2 experienced co-investigators (15+ years of expertise in CEUS imaging) blinded to the surgical results and contrast-enhanced MRI evaluations, to allow repeatability to be assessed. All ultrasound studies will be rated on a quasi-continuous scale from 0 to 100 ranging from “no lesion seen (no findings)” over “definitely benign,” “indeterminate” to “definitely malignant.” Using a quasi-continuous 100-point rating scale has an intuitive probabilistic interpretation and is known to improve the assessment of the capabilities of the imaging modes studied [Wagner et al. 2001]. The SHI clips will be processed to produce CMI-SHI images [Dave & Forsberg 2009; Dave et al 2010], which will also be read by the blinded readers. Finally, sensitivity, specificity and accuracy will be calculated for all imaging modalities (baseline and SHI as well as MRI) and compared to the RMI values used to select patients for surgery [Ferrazzi et al. 1997; 2005; Moolthiya & Yuenyao 2009].

Off-line SHI TICs will be created on a pixel by pixel basis. Parametric images will be generated showing time-to-peak, perfusion rate, peak intensity (calculated in dB as the ratio of the peak to the baseline values) and area under the curve (AUC) in the area of greatest vascularity as well as parameters across the mass (based on the data from second infusion) [Eisenbrey et al. 2011b]. The TIC parameters will be compared to the lesion characterization of the other imaging modalities with pathology as the reference standard. It is our hypothesis that these new SHI based biomarkers will improve our capabilities to characterize ovarian cancers. Results will also be compared to MRI enhancement kinetics and imaging assessments obtained as part of the subjects’ standard of care.

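### H2 names no SHI biomarker for its AUC target, and AUCs from the planned logistic models come from the 45 subjects used to fit them (7–9 cancers), without internal validation

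*Combined protocol and SAP*

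**What the plan says.** The primary objective (section 2) begins "To develop qualitative subharmonic imaging (SHI) or SHI-derived quantitative biomarkers", so developing biomarkers is part of the declared purpose.

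Section 7.2.1 then sets two AUC hypotheses. For both, the target reads "As an initial end-point we speculate that an area under the ROC curve of 0.75 or better will be achieved by EV SHI". H1 concerns EV SHI in general. H2 states that "EV SHI biomarkers will improve the characterization of benign and malignant adnexal masses" relative to standard ultrasound, MRI or other clinical parameters, whose low-end performance is given as a figure "which is on the order of 0.70 to 0.72". No biomarker is named.

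Section 6.4 describes the measures that could fill the role:

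- **Ratings.** "All ultrasound studies will be rated on a quasi-continuous scale from 0 to 100", and grayscale with SHI is one of the sets rated.
- **A second kind of SHI reading.** "The SHI clips will be processed to produce CMI-SHI images", and the blinded readers assess these as well.
- **Curve parameters.** "Parametric images will be generated showing time-to-peak, perfusion rate, peak intensity" and area under the time-intensity curve, in the most vascular area. Parameters across the whole mass, from the infusion, are mentioned too but not listed.
- **Readers.** "Each case will be read independently by the 2 experienced co-investigators". No rule for combining the two is given.

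Section 7.2.2 plans ROC comparisons of the imaging tests. It also plans logistic regression with ROC analysis for the incremental value of imaging diagnosis, morphology and RMI. Section 7.2.3 expects 15–20% cancers among 45 subjects. Sections 7.2.1 to 7.2.3 contain no selection rule, no direction for the curve parameters, no fixed predictor list and no internal validation.

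**The concern.** Two different mechanisms push an AUC upward here.

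The first is overfitting. A logistic model tuned to 7–9 cancers separates those same subjects better than it would separate new ones. This follows from the analysis as written if the ROC curve is drawn from the fitted scores without correction. It bears directly on incremental validity, because a larger model gains apparent AUC even when the added predictor is useless.

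The second is selection. H2 leaves several candidates open, so a later report could present the highest AUC as the H2 result. That value would be too high on average.

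Section 7.2.3 says the pilot is meant to supply data for a larger study. An inflated AUC carried forward could mislead both the choice of biomarker and the planning of that study.

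**Working it through.** **Inputs.** From section 7.2.3: 45 subjects, 0.15 × 45 = 6.75 and 0.20 × 45 = 9, so 7–9 cancers and 36–38 benign masses. From section 7.2.1: target 0.75 and comparators 0.70–0.72, a margin of 0.75 − 0.72 = 0.03 to 0.75 − 0.70 = 0.05. From section 6.4: 4 curve parameters alone, 4 + 2 = 6 with the two readings, or 8 + 2 = 10 if the same four are also taken across the mass. That last count is an inference, not the plan's figure.

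**The plan's own precision figure.** The only one concerns H3. Fisher's z gives tanh(atanh 0.70 ± 1.96/√42) = (0.51, 0.82), which agrees with section 7.2.3. No such figure is given for the AUC. By the Hanley–McNeil formula, a single pre-named measure with AUC 0.75 has a 95% CI of about 0.53–0.97 with 7 cancers and 0.55–0.95 with 9. That is imprecision, not bias.

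**Fitted model.** Simulated trials of 45 used independent normal predictors, with cancers shifted by √2·Φ⁻¹(AUC) on each informative one. Apparent AUC is computed in the fitting data; true AUC is that of the same fitted score in new subjects. Each informative predictor has an assumed AUC of 0.70.

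| Predictors | Apparent (7 / 9 cancers) | True (7 / 9) | Bias |
|---|---|---|---|
| 2 informative | 0.79 / 0.79 | 0.75 / 0.75 | 0.04–0.05 |
| 2 informative + 2 noise | 0.83 / 0.82 | 0.71 / 0.72 | 0.10–0.12 |
| 1 informative + 1 noise | 0.73 / 0.73 | 0.66 / 0.67 | 0.06–0.07 |
| 1 informative + 2 noise | 0.76 / 0.75 | 0.64 / 0.65 | 0.10–0.12 |
| 1 informative + 3 noise | 0.78 / 0.77 | 0.63 / 0.64 | 0.13–0.15 |

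The bias is thus about 0.04–0.12, and 0.13–0.15 when only one of four predictors is informative. In the last three rows each further noise predictor raises the apparent AUC while the true AUC falls.

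**Selected biomarker.** The simulations used equally correlated normal markers with direction fixed. Bias is the highest observed AUC minus the true AUC of the marker chosen; ranges cover 7 and 9 cancers.

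- One named measure has no bias. If truly 0.65, it reaches 0.75 in 17–20% of trials.
- Best of 4 to 10, all truly 0.65, correlation 0.5–0.8: bias about 0.05–0.12. For 6 to 10 candidates 0.75 is reached in 36–63% of trials.
- Best of 6 to 10, all truly 0.65, correlation 0.9–0.95: bias 0.03–0.06.
- One leader at 0.75 with the rest at 0.60, or at 0.80 with the rest at 0.65, 6 to 10 candidates: bias about 0.04–0.08 at correlation 0.5, 0.01–0.02 at 0.8, and under 0.005 at 0.9.
- H1, better of two readings both truly 0.65, correlation 0.5–0.8: bias 0.03–0.05.

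**The case against.** The strongest defence is that this is a declared development pilot. The AUC targets are called speculative, no go/no-go decision or later sample size is tied to 0.75, and sections 7.2.3 and the synopsis disclaim definitive answers. Exploring several biomarkers is the purpose. Section 6.4 says the curve parameters will be compared with the other modalities against pathology, which can be read as reporting all of them.

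Much of this stands. A reader might infer that the plan intends to pick the best biomarker and present it as the H2 result. The documents do not say so; they only leave it open. A reader might also infer that selection bias must swamp the 0.03–0.05 margin over the comparators. It need not. High correlation is plausible because the processed images come from the SHI clips and the parameters share the same curves, and with a clear leader the bias can be close to nil. Nor should 0.75 be used to judge the logistic models, since section 7.2.1 sets that target for EV SHI only. For H1, the 0–100 rating of grayscale with SHI is the natural measure.

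What does not stand is the pilot disclaimer as a full answer. It concerns lack of power, that is, imprecision. It does not address a systematic upward error in figures meant for planning the next study. The fitted-model bias also arises without any choice among biomarkers.

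**Conclusion.** The point holds, centred on H2 and the fitted models. It deserves a change to the analysis section but does not undermine the study.

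- **Fitted models:** biased upward as planned, by about 0.04–0.12 for 2–4 predictors and up to 0.15 if only one of four is informative. This assumes informative predictors at AUC 0.70, independent predictors, and ROC curves drawn from uncorrected fitted scores. The plan does not fix the number of predictors.
- **H2 biomarker:** biased only if the best one is reported as the result. The bias is then about 0.05–0.12 for 4–10 equally good candidates (true AUC 0.65, correlation 0.5–0.8), and near 0 to 0.08 if one clearly leads. It can, but need not, exceed the plan's margin. The true AUCs and correlations are assumptions.
- **H1:** minor. What is open is whether the processed-image reading counts and how the two readers are combined.

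**What to change.** **Section 7.2.1**, before pathology is merged: name one SHI biomarker for H2, with its region and direction, and confirm for H1 which reading is used and how the two readers are combined. The choice is the sponsor's. Label the other measures exploratory.

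**Section 7.2.2**: report the AUC of every candidate with a 95% CI. For any biomarker selected on the data, and for any fitted logistic model, also report an optimism-corrected AUC from a bootstrap that is stratified by pathology and repeats the selection or fitting in each resample. State that it is imprecise with 7–9 cancers.

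**Cost**: wording and some programming, no extra data. Reported AUCs will be somewhat lower, and the correction is partial.

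- *Selected biomarker* (best of 6 or 10, all truly 0.65): the mean AUC fell in simulation from 0.71–0.77 to 0.67–0.70, leaving 0.02–0.05 of upward bias. Root mean squared error fell from 0.111–0.147 to 0.098–0.113.
- *Logistic model* (2 or 4 predictors, one truly 0.70): the mean fell from 0.73–0.79 to 0.67–0.69, against a true 0.63–0.67. With four pure-noise predictors the residual bias is up to 0.09.
- The corrected AUC has a standard deviation of about 0.08–0.13 across simulated trials.
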